4.3.1.3 Best Overall Response

Patients not meeting the criteria for BOR, including patients with no response assessments (for whatever reason) will be considered non-responders.

Following the estimand framework (ICH 2020), the attributes of the estimand for the secondary endpoint are defined as follows:

- **Population:** As defined for the primary estimand in Section 4.2.1.
- **Variable:** BOR, defined as the proportion of patients with a CR or PR, as determined by the investigator according to RECIST v1.1.
- **Treatment:** As defined for the primary estimand in Section 4.2.1
- **Intercurrent events and Handling strategy:**
 - As defined for the primary estimand in Section 4.2.1
 - **ICE Handling Strategy:** Following treatment policy, all the ICE's will be ignored and tumor assessment data collected after the ICE will be included in the BOR analysis.
- **Population-level summary:** Difference in proportion

Analysis methodology is as outlined for ORR.

4.3.1.4 Clinical Benefit Rate

Patients not meeting the criteria for CBR, including patients with no response assessments (for whatever reason) will be considered non-responders.

Following the estimand framework (ICH 2020), the attributes of the estimand for the secondary endpoint are defined as follows:

- **Population:** As defined for the primary estimand in Section 4.2.1.
- **Variable:** CBR, defined as the proportion of patients with a CR, PR, and/or SD for at least 24 weeks, as determined according to RECIST v1.1.
- **Treatment:** As defined for the primary estimand in Section 4.2.1
- **Intercurrent events and Handling strategy:**
 - As defined for the primary estimand in Section 4.2.1
 - ICE Handling Strategy: Following treatment policy, all the ICE's will be ignored and tumor assessment data collected after the ICE will be included in the CBR analysis.
- **Population-level summary:** Difference in proportion

Analysis methodology is as outlined for ORR.

4.3.1.5 Duration of Objective Response

The analysis of DOR will include only patients who achieved an objective response.

Following the estimand framework (ICH 2020), the attributes of the estimand for the secondary endpoint are defined as follows:

- **Population:** All randomized patients who had an objective response
- **Variable:** DOR is defined as the time from the first occurrence of a PR or CR to the first occurrence of disease progression as determined by the investigator according to RECIST v1.1 or death from any cause (whichever occurs first)
- **Treatment:** As defined for the primary estimand in Section 4.2.1
- **Intercurrent events and Handling strategy:**
 - As defined for the primary estimand in Section 4.2.1
 - ICE Handling Strategy: Following treatment policy, all the ICE's will be ignored and tumor assessment data collected after the ICE will be included in the DOR analysis
- **Population-level summary:** Hazard ratio

Analysis methodology is as outlined for the primary endpoint, PFS. Data for patients without the occurrence of disease progression or death will be censored at the time of the last tumor assessment. Comparisons between treatment arms using stratified and unstratified log rank test will be made for descriptive purposes. Because the determination of DOR is based on a non-randomized subset of patients, formal hypothesis testing will not be performed.

4.3.2 Supportive Secondary Endpoint

4.3.2.1 Patient Reported Outcomes

To evaluate TTCD in pain, the “worst pain” item from the BPI-SF will be assessed. TTCD is defined as the time from randomization to the first documentation of a 2-point

increase from baseline in “worst pain” held for at least two consecutive cycles, or an initial increase followed by death or treatment discontinuation within three weeks from the last assessment. A 2-point change is defined as clinically meaningful ([Mathias et al. 2010](#)).

TTCD in physical function (PF), role function (RF), and global health status (GHS)/health-related quality of life (HRQoL) will be assessed. TTCD is defined as the time from randomization to the first documentation of a ≥ 10 -point decrease from baseline in the specific scale held for at least two consecutive cycles, or an initial decrease followed by death or treatment discontinuation within three weeks from the last assessment:

- Physical Function (items 1 through 5)
- Role Function (items 6 and 7)
- Global Health Status (GHS)/Quality of Life (QoL) (items 29 and 30)

A ≥ 10 -point change is defined as a clinically meaningful difference ([Osoba et al. 1998](#)) on all scales of the EORTC-QLQ-C30.

For both BPI-SF and EORTC-QLQ-C30, patients who do not have an observed deterioration at the time of the clinical data cutoff will be censored at the last non-missing assessment date. Patients without a post-baseline assessment will be censored at the time of randomization.

4.4 EXPLORATORY ENDPOINT(S) ANALYSIS

The exploratory efficacy objective for this study is to evaluate the efficacy of inavolisib in combination with palbociclib and fulvestrant compared with placebo plus palbociclib and fulvestrant on the basis of the following endpoints:

- Time to end of next-line treatment (proxy for time to second objective disease progression [PFS2]), defined as the time from randomization to end or discontinuation of next-line treatment, or death from any cause (whichever occurs first). Data for patients without the occurrence of second objective disease progression or death and patients who have not started next-line treatment will be censored at the last date they were known to be alive. Data from patients without post-baseline information will be censored at the date of randomization. Analysis methodology is as outlined for the primary endpoint, PFS in Section [4.2.2](#).
- Time to first Skeletal related event (SRE), defined as the time from randomization to the first occurrence of an SRE. An SRE is a pathologic fracture, radiation therapy to bone, cancer-related surgery to bone, or spinal cord compression. Data from patients without the occurrence of an SRE will be censored at the last valid visit. Data from patients without post-baseline information will be censored at the date of randomization. Analysis methodology is as outlined for the primary endpoint, PFS in Section [4.2.2](#).

- Mean scores and mean change from baseline in functional scores (physical, role, cognitive, emotional, and social), GHS/QoL, disease and treatment–related symptom scores.

Summary statistics (mean, standard deviation, median, 25th and 75th percentiles, and range) of scores will be reported for the "worst pain" item of the BPI-SF, as well as all linear transformed scores for scales (symptoms, functional domains, and GHS/QoL) of the QLQ-C30 and QLQ-BR23 questionnaires for each assessment time point. The mean change of the linear transformed scores from baseline (and 95% CI using the normal approximation) will also be analyzed for each treatment arm.

In the event of incomplete data for all questionnaire scales, if more than 50% of the constituent items are completed, a prorated score will be computed consistent with the scoring manuals and validation papers (see protocol). For scales with less than 50% of the items completed, the scale will be considered as missing in accordance with the EORTC scoring manual guidelines.

PRO completion, compliance rates, and reasons for missing data will be summarized at each time point by treatment arm for each measure in FAS population. The compliance rate will be based on the total number of patients expected to complete the questionnaire at a particular time point.

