6.4.3 Exploratory Efficacy Endpoints

6.4.3.1 Exploratory Clinical Outcomes

- Time to end of next-line treatment (proxy for time to second objective disease progression [PFS2]), defined as the time from randomization to end or discontinuation of next-line treatment, or death from any cause (whichever occurs first). Data for patients without the occurrence of second objective disease progression or death and patients who have not started next-line treatment will be censored at the last date they were known to be alive. Data from patients without post-baseline information will be censored at the date of randomization. Analysis methodology is as outlined for the primary endpoint, PFS.
- Time to first SRE, defined as the time from randomization to the first occurrence of an SRE. An SRE is a pathologic fracture, radiation therapy to bone, cancer-related surgery to bone, or spinal cord compression. Data from patients without the occurrence of an SRE will be censored at the last valid visit. Data from patients without post-baseline information will be censored at the date of randomization. Analysis methodology is as outlined for the primary endpoint, PFS.

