4.2.2 Main Analytical Approach for Primary Endpoint

If participants have any intercurrent event(s), then the strategies defined as defined in Section 4.2.1 to handle the intercurrent events will be implemented. Data for participants without the occurrence of disease progression or death as of the clinical cutoff date (CCOD) will be censored at the time of the last tumor assessment prior to the CCOD (or at the time of randomization if no tumor assessment was performed after the baseline visit).

PFS will be compared between treatment arms using the two-sided stratified logrank test at the 0.05 level of significance.

The hazard ratio will be estimated using a stratified Cox proportional hazards model. The 95% CI for the hazard ratio will be provided. The stratification factors used will be the same as the randomization stratification factors (as entered in IxRS, Section 1.2.1). Results from an unstratified analysis (see Section 4.2.3) will also be provided as sensitivity analysis. For each treatment arm, Kaplan-Meier methodology will be used to estimate the median PFS, and the Brookmeyer-Crowley method will be used to construct the 95% CI for the median PFS. Kaplan-Meier curves will also be produced.

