4.3.1 Key Secondary Endpoint

4.3.1.1 Overall Survival

The secondary comparison of interest is the hazard ratio of OS.

OS is defined as the time from randomization to death from any cause. Data for patients who are alive at the time of the analysis data cutoff will be censored at the last date they

were known to be alive. Data from patients without post-baseline information will be censored at the date of randomization.

Analysis methodology is as outlined for the primary endpoint, PFS.

An interim analysis of OS will be performed at the time of the primary analysis of PFS. In addition to the fixed sequence testing approach described before, a group-sequential design (Lan-DeMets with O'Brien-Fleming stopping boundaries) will be used to control the overall type I error rate ([Lan and DeMets 1983](#)) for the OS interim analysis and a final (event-driven, after approximately 153 OS events) analysis of OS.

The median OS in the control arm is assumed to be 35 months and the median OS in the experimental treatment arm is assumed to be 50 months, equating to a hazard ratio of 0.7. At the time of the primary PFS analysis, on the basis of the above assumptions, 105 OS events are expected to have occurred and 153 OS events for the final analysis of OS are expected to have occurred 19 months later. With the above assumptions, the cumulative power at the interim and final OS analysis is 25% and 59%, respectively. This statistical analysis plan for OS has been designed to provide appropriate OS information and maturity to support the primary PFS endpoint. However, if appropriate, additional exploratory analyses of OS may be conducted after the final analysis at time points defined through study milestones such as Health Authority interactions.

Following the estimand framework ([ICH 2020](#)), the attributes of the estimand for the secondary endpoint are defined as follows:

- **Population:** As defined for the primary estimand in Section [4.2.1](#)
- **Variable:** OS defined as time from randomization to death from any cause.
- **Treatment:** As defined for the primary estimand in Section [4.2.1](#)
- **Intercurrent events and Handling strategy:**
 - Start of non-protocol anticancer therapy prior to OS. Following treatment policy, the ICE will be ignored.
 - Early discontinuation from study treatment for any reason prior to an OS event. Following treatment policy, the ICE will be ignored.
- **Population-level summary:** Hazard ratio for OS.

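### SAP 4.4: read literally, the PFS2-proxy censoring sentence censors patients whom the endpoint definition counts as events

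*SAP*

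**What the plan says.** SAP section 4.4 introduces time to end of next-line treatment as a proxy for PFS2, "defined as the time from randomization to end or discontinuation of next-line treatment, or death from any cause (whichever occurs first"). Death counts as an event, and nothing requires that next-line treatment was started.

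The sentence that follows sets the censoring. It covers those without second objective progression or death, and a further group: "patients who have not started next-line treatment will be censored at the last date they were known to be alive". Protocol section 6.4.3.1 has the same definition, and its censoring sentence covers the same two groups: "Data for patients without the occurrence of second objective disease progression or death and patients who have not started next-line treatment". The SAP states that it supersedes the protocol's analyses, but since the texts agree, neither settles the meaning of the other.

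The endpoint is analysed by the PFS methods of SAP section 4.2.2: stratified log-rank test, stratified Cox hazard ratio and Kaplan-Meier medians.

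**The concern.** The definition and the censoring sentence disagree in two places.

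1. The second censored group is everyone who has not started next-line treatment, dead or alive. A patient who dies before next-line treatment meets the definition and also falls in that group.
2. The first censored group is described by the absence of second objective progression or death. The defined event is the end or discontinuation of next-line treatment, which is different. A living patient who has ended next-line treatment without a documented second progression has had the event, yet fits the description of the censored group.

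Censoring deaths is informative censoring and makes Kaplan-Meier estimates too long. Two programmers working from this text could produce different datasets, which a SAP should prevent.

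**Working it through.** The plan gives no event count, power or sample size for this endpoint, so it has no figure of its own to reproduce. The main check is a comparison of texts.

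**Classification at the cutoff**

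| Patient | By the definition | By the censoring sentence, literally |
|---|---|---|
| Died, next-line treatment never started | Event | Censored (second group) |
| Alive, next-line treatment ended, no second progression documented | Event | Censored (first group) |
| Alive, still on next-line treatment, no second progression | No event | Censored (first group) |
| Alive, next-line treatment not started | No event | Censored |
| Died after starting next-line treatment | Event | Not censored |

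The first two rows conflict. The second is not a rare case by design: protocol sections 3.1.1, 4.5.5 and 4.6.1 stop scheduled tumor assessments at progression or at the start of another anti-cancer therapy. No imaging is then scheduled that would document a second progression.

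**Could the two conditions be read as one joint condition?** Suppose a patient is censored only if there is no second progression or death and also no start of next-line treatment. Both conflicts disappear, but living patients still on next-line treatment then have neither an event nor a censoring rule. That reading does not repair the text.

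**Comparison with the SAP's other rules.** For PFS (section 4.2.2): "Data for participants without the occurrence of disease progression or death as of the clinical cutoff date (CCOD) will be censored". For OS (section 4.3.1.1): "Data for patients who are alive at the time of the analysis data cutoff will be censored". Duration of response (section 4.3.1.5) likewise censors only patients without progression or death. None of these can censor a patient who has had the event.

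**Number of deaths affected.** Inputs from SAP section 4.3.1.1. For the primary PFS analysis: "105 OS events are expected to have occurred". For the later, event-driven look at survival: "153 OS events for the final analysis of OS are expected to have occurred 19 months later". The share of deaths that precede next-line treatment is not in the documents; 5% to 40% is an assumption.

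Deaths censored = expected deaths × share

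- Primary PFS analysis: 105 × 0.05 = 5.25, about 5; 105 × 0.40 = 42.
- Final OS analysis: 153 × 0.05 = 7.65, about 8; 153 × 0.40 = 61.2, about 61.

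**Effect on the estimates (illustrative simulation).** From the plan: exponential times with medians 11 and 16.9 months (11 / 0.65 = 16.9), here used as the time to leaving study treatment; accrual over 43 months; cutoff at 50 months. Assumed: uniform accrual, a median of 6 months from then to the end of next-line treatment, and no dropout. The shares here are of patients, not of deaths. The ratio is events per unit of follow-up time, experimental over control, standing in for the Cox hazard ratio. Only the first conflict is modelled.

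| Die before next-line treatment, control / experimental | Events censored per 320 patients | Control median, definition → rule (months) | Experimental median, definition → rule (months) | Ratio, definition → rule |
|---|---|---|---|---|
| 5% / 5% | 11.5 | 19.7 → 20.6 | 26.0 → 27.2 | 0.709 → 0.709 |
| 10% / 10% | 22.8 | 19.3 → 21.2 | 25.5 → 27.8 | 0.710 → 0.709 |
| 5% / 15% | 21.6 | 19.8 → 20.6 | 25.0 → 28.7 | 0.747 → 0.649 |
| 15% / 5% | 23.8 | 18.9 → 21.7 | 26.0 → 27.1 | 0.671 → 0.766 |

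With 10% in each arm the medians rise by 21.2 − 19.3 = 1.9 and 27.8 − 25.5 = 2.3 months, and the ratio is unchanged to two decimals. With unequal shares the ratio moves by about 0.10, in a direction set by which arm has more such deaths.

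**The case against.** The strongest reply is that nobody meant to censor deaths. The definition, one sentence earlier, makes death an event, and censoring at the date last known alive suggests living patients. The mention of patients who have not started next-line treatment may only clarify that they too are censored if event-free. Likewise, second objective progression may be shorthand for the proxied event; taken literally it would leave little but deaths as events and defeat the proxy.

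Much of this stands as an account of intent. A reader might infer that the sponsor chose to censor deaths. The documents do not say so: that outcome follows from the literal wording, and the definition points the other way. But intent does not repair the sentence. The repeated reference to patients sets up a second, separate group, and the joint reading leaves a gap.

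A reader might also infer that the treatment comparison is biased. That needs the share of deaths before next-line treatment to differ between arms, and nothing in the documents indicates that it does.

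**Conclusion.** The censoring sentence conflicts with the endpoint definition in both documents and should be corrected. This is an error of wording; it is not evidence of a deliberate analysis choice.

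Under the literal reading, about 5 to 42 of the 105 deaths expected at the primary PFS analysis would become censored observations. That range rests on the assumed share of 5% to 40% and on the SAP's own OS assumptions behind the 105. Arm medians would lengthen, and the hazard ratio would change materially only with unequal shares. The second conflict, over patients who have ended next-line treatment, cannot be sized from the documents.

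A reader might infer that the trial's main conclusions are exposed. They are not. The endpoint is exploratory and absent from the fixed testing sequence in SAP section 4.3. Deaths count as events in both PFS and OS, and no alpha, power or sample size depends on this rule.

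**What to change.** Replace the censoring sentence in SAP section 4.4 and protocol section 6.4.3.1 with wording such as:

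*Patients who by the clinical cutoff date have neither ended or discontinued next-line treatment nor died are censored when last known alive, whether or not next-line treatment was started. For all other patients, the event date is the earlier of the end or discontinuation of next-line treatment and death.*

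This restores deaths before next-line treatment as events and uses the defined event throughout. It also applies the cutoff, and a patient who ends next-line treatment and later dies keeps the earlier date. The existing rule for patients without post-baseline information can stay.

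The cost is one sentence in each document, best made before unblinding for the primary PFS analysis. No new procedure is needed: protocol section 3.1.1 already collects survival and subsequent anti-cancer therapies about every 3 months.

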4.5 SAFETY ANALYSES

The safety analysis population consists of all patients who received at least one dose of study drug and is based on the treatment the patients actually received; that is, all patients who received at least one dose of inavolisib are included in the inavolisib plus palbociclib and fulvestrant group and all patients who received any palbociclib or fulvestrant (and no inavolisib) are included in the placebo plus palbociclib and fulvestrant group.

The safety objective for this study is to evaluate the safety of inavolisib plus palbociclib and fulvestrant compared with placebo plus palbociclib and fulvestrant on the basis of the following endpoints:

- Incidence and severity of adverse events, with severity determined according to National Cancer Institute Common Terminology Criteria for Adverse Events, Version 5.0 (NCI CTCAE v5.0)
- Change from baseline in targeted vital signs (e.g., pulse rate, blood pressure, body weight)
- Change from baseline in targeted clinical laboratory test results
- Change from baseline in ECG parameters

Safety will be assessed through summaries of exposure to study treatment, adverse events, changes in laboratory test results, and changes in vital signs and ECGs.

Additionally, a shift table of selected laboratory tests (e.g., FBG, HbA1C, liver enzymes) will be used to summarize the baseline and maximum post-baseline severity grade. Changes in vital signs and ECGs will be summarized.

4.5.1 Extent of Exposure

Study treatment exposure (such as treatment duration, total dose received, and number of cycles and dose modifications) and dose intensity will be summarized with descriptive statistics.

4.5.2 Adverse Events

All verbatim adverse event terms will be mapped to Medical Dictionary for Regulatory Activities (MedDRA) thesaurus terms, and adverse event severity will be graded according to NCI CTCAE v5.0. All AEs will be coded using the current version of MedDRA (which is anticipated to be Version 26.0) at the time of database closure.

All adverse events, serious adverse events, adverse events leading to death, adverse events of special interest, selected AEs and adverse events leading to study treatment discontinuation or dose modification that occur on or after the first dose of study treatment (i.e., treatment-emergent adverse events) will be summarized accordingly. For events of varying severity, the highest grade will be used in the summaries. Deaths and cause of death will be summarized.

4.5.3 Additional Safety Assessments

4.5.3.1 Laboratory Data

Relevant laboratory values will be summarized by treatment arm over time, with NCI CTCAE v5.0 Grade 3 and Grade 4 values identified, where appropriate (e.g., Hy's law, AST/ALT elevation, FBG). Summary tables of clinically relevant shifts in NCI CTCAE v5.0 grades (Grades ≤ 2) at baseline to the worst post-baseline (Grade ≥ 3) value will be presented.

A Hy's law analysis will be provided: the finding of an elevated ALT or AST ($>3\times$ baseline value) in combination with either an elevated total bilirubin ($> 2\times$ ULN) or clinical jaundice in the absence of cholestasis or other causes of hyperbilirubinemia is considered to be an indicator of severe liver injury (as defined by Hy's Law).

